Department of Critical Care, Division of Anesthesiology and Critical Care,
The University of Texas M. D. Anderson Cancer Center
[contact]

Pharmacological assistance

[name], BCNSP,
Clinical Pharmacist Specialist, Pharmacy Clinical Programs,
[name]
John Mendelsohn Faculty Center, FC6.3014
Pharmacy Clinical Programs, The University of Texas M. D. Anderson Cancer Center
Office [name]
[contact]

Clinical Nutrition assistance

[name] BS, MS

Clinical Nutrition Specialist, Clinical Nutrition
[name]
Department of Critical Care, Division of Anesthesiology and Critical Care,
The University of Texas M. D. Anderson Cancer Center
[contact]

[name] BS, MS
Clinical Nutrition Specialist, Clinical Nutrition
[name]
Department of Critical Care, Division of Anesthesiology and Critical Care,
The University of Texas M. D. Anderson Cancer Center
[contact]

Statistical collaborator

[name]
Senior Statistical Analyst, Biostatistics
The University of Texas M. D. Anderson Cancer Center
T. Boone Pickens Academic Tower (FCT4.5005)
[name]
[contact]

SUMMARY TABLE

Title	Early Metabolic Resuscitation: A Potential Solution to Multi-Organ Dysfunction Syndrome in Septic Shock
Question	Is Early Metabolic Resuscitation the Solution to Multi-Organ Dysfunction Syndrome in Patients Diagnosed with Septic Shock?
Protocol Number	2018-0986
Study Size (# of patients)	The sample size will include 112 patients (56 patients randomly assigned to each study group).
Study Design	This is a prospective, single center, un-blinded, randomized controlled trial. Patients will be stratified by type of malignancy, and blocking will be used to ensure balance between study groups. Patients will be randomized to either Early Metabolic Resuscitation with Standard of Care (SC + EMR) or Standard of Care alone (SC). The randomization will be conducted through CORe.
Primary Objective	The primary objective of this study is to assess the efficacy of administering Early Metabolic Resuscitation with Standard of Care (SC + EMR) in patients diagnosed with septic shock for reducing 28-day mortality versus using the Standard of Care alone (SC).
Secondary Objective	
 1. To assess whether Early Metabolic Resuscitation with standard of care (SC + EMR) is an effective strategy to reduce ICU mortality, hospital mortality, and 90-day mortality relative to SC. ICU mortality is defined as mortality at ICU discharge. 2. To compare the time to death from any cause between patients administered SC + EMR versus SC after being diagnosed with septic shock. 3. To assess whether SC + EMR is an effective strategy to reduce complications of septic shock such as: i) acute kidney injury, ii) dialysis requirements, iii) need for cardiovascular support or days on vasopressors, iv) need for invasive ventilation, days on ventilator support, v) duration of ICU stay, and vi) duration of hospital stay versus SC.

	
4. To describe the presence of any adverse effects between the two study groups (SC + EMR group vs SC group); thus, characterizing their safety.

Inclusion Criteria	
 1. Adult patients aged 18 years old or older 2. Admitted to the adult medical intensive care unit (MICU) 3. Diagnosis of Septic Shock within 12 hours of ICU admission, unless the patient is already admitted to the ICU, defined as meeting criteria for sepsis in addition to the following: 
 a. Vasopressor therapy needed to elevate MAP ≥ 65 mmHg. o Lactate > 1 mmol/L (9 mg/dL) and/or Base excess <-2 after adequate fluid resuscitation 4. Sequential Organ Failure Assessment (SOFA) score meeting the following requirements 
 a. Cardiovascular SOFA ≥ 2 b. Total SOFA score ≤ 12 5. Patients meeting the above and not able to tolerate enteral nutrition above 70% of their estimated daily caloric need
Study Details	
Primary Endpoint	The primary endpoint is 28-day mortality, defined during the time from the day SC+EMR or SC was first administered until a patient dies or is followed through 28 days (whichever comes first).
Sample Size Justification	The rate of 28 day mortality from septic shock at the UT MD Anderson Cancer Center was 70% in 2017. With the objective of decreasing this rate to 40%, a sample size of 112 patients (56 per group) provides 90% power to detect a 30% absolute reduction in the rate of 28-day mortality using a two-sided chi-square test at the 0.05 significance level. We plan to use stratified randomization in a 1:1 fashion to assign patients into two groups, and a fixed block size consisting of 4

	patients will be used. The randomization will be conducted in CORe.
Brief Analysis Plan	
Descriptive statistics including the mean, standard deviation, median, and range will be used to summarize continuous variables. Frequency counts and percentages will be used to summarize categorical variables. Categorical variables, including 28-day mortality, will be compared between intervention groups using a chi-square test, or Fisher's exact tests if more appropriate. Continuous variables will be compared between intervention groups using an independent samples t-test, or Wilcoxon rank-sum test if more appropriate.
 
Logistic regression will be used to assess relationships between patient characteristics and binary study outcomes of interest. Continuous variables, including the time on cardiovascular support and time on ventilator, will be compared using t-tests or Wilcoxon rank-sum tests.
 
Time to event analyses will be conducted using Cox proportional hazards regression. For 28-day mortality, living patients will be censored at the end of 28 day follow-up after the treatment was given. For overall survival, patients will be followed until time of death or date of last follow-up (maximum 6 months). Kaplan-Meier plots will be used to visually compare time to death from any cause between intervention arms followed by a log-rank test to compare survival distributions.

1.0 STUDY OBJECTIVES

1.1 Primary Objective:

To assess the efficacy of administering Early Metabolic Resuscitation with Standard of Care (SC + EMR) in patients diagnosed with septic shock for reducing 28-day mortality versus using the Standard of Care alone (SC). Twenty-eight day mortality is defined during the time from the day SC+EMR or SC was first administered until a patient dies or is followed through 28 days (whichever comes first).

1.2 Secondary Objectives:

1. To assess whether Early Metabolic Resuscitation with standard of care (SC + EMR) is an effective strategy to reduce ICU mortality, hospital mortality, and 90-day mortality of septic shock patients relative to SC. ICU mortality is defined as mortality at ICU discharge relative to SC.
2. To compare the time to death from any cause between patients administered SC + EMR versus SC after being diagnosed with septic shock.
3. To assess whether SC + EMR is an effective strategy to reduce complications of septic shock such as: i) acute kidney injury, ii) dialysis requirements, iii) need for cardiovascular support or days on vasopressors, iv) need for invasive ventilation, days on ventilator support, v) duration of ICU stay, and vi) duration of hospital stay versus SC.
4. To describe the presence of any adverse effects between the two study groups (SC + EMR group vs SC group); thus, characterizing their safety.

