5.0 SELECTION AND ENROLLMENT OF PARTICIPANTS

5.1 Inclusion Criteria

- Adult patients aged 18 years old or older
- Admitted to the adult medical intensive care unit (MICU)
- Diagnosis of Septic Shock within 12 hours of ICU admission , unless the patient is already admitted to the ICU, defined as meeting criteria for sepsis in addition to the following:
 - Vasopressor therapy needed to elevate MAP \geq 65 mmHg.
 - Lactate $>$ 1 mmol/L (9 mg/dL) and/or Base excess $<$ -2 after adequate fluid resuscitation.
- Sequential Organ Failure Assessment (SOFA) score meeting the following requirements
 - Cardiovascular SOFA \geq 2
 - Total SOFA score \leq 12
- Patients meeting the mentioned inclusion criteria and not able to tolerate enteral nutrition above 70% of their estimated daily caloric need

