6.0 STUDY INTERVENTIONS

6.1 Description of study groups

There will be two arms or groups in this study

1. **(Standard of Care: SC)** - follow institutional ICU management algorithm for septic shock
2. **(Early metabolic resuscitation with Standard of Care: SC + EMR)** - infusion of EMR solution with Standard of Care

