6.4 Adherence Assessment

Adherence will be defined as continuous infusion of study solutions 90% of the time from onset of study until cessation. This will be assessed via the electronic patient record, which will record infusion stop/start times.

Patients who have requested to be withdrawn from the study or achieve Comfort Care status during ICU stay will be removed from the study. Those who die or begin renal replacement will be followed up but the interventions will be stopped.

[figure not shown]

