8.2 Management of anticipated adverse events

1. Fluid overload

This is considered to be very unlikely as sepsis and particularly septic shock are conditions where aggressive fluid resuscitation is recommended (30). The amount of fluid administered daily is considered to be relatively conservative. Furthermore, patients requiring renal replacement therapy will be excluded for further intervention, so harm from this intervention is highly unlikely.

There is no consensus or standard definition of fluid overload. We ask physicians to discontinue other fluids in preference to the EMR investigation fluids when possible. If there is severe fluid overload whereby the primary team finds it necessary to discontinue the fluid, then the patient will be withdrawn. It is not considered acceptable to slow the rate of the study solution – if this is felt to be essential, then the study solutions will be weaned and fluid management left to the care of the primary team.

2. Electrolyte abnormalities

a. Hyperkalemia (see appendix)

- i. Once potassium reaches ≥ 5 mmol/L EMR solution I (with potassium) has to be substituted with EMR solution II (without potassium) – EMR II has to continue despite hyperkalemia. EMR I has to replace EMR II once potassium levels reach ≤ 4 mmol/L
- ii. Potassium levels over ≥ 5.5 mmol/L have to be treated with standard ICU protocol. If EMR I is infused this has to be recorded as an adverse event and EMR I must be immediately replaced with EMR II

b. Hypokalemia ($K \leq 3$) (see appendix)

The ICU patients typically demonstrate low serum potassium level between 3 and 3.5, which are typically treated using the standard ICU electrolyte replacement protocol. Only serum potassium level of ≤ 3 will be reported as an adverse event.

c. Hypernatremia (Na >150)

- i. Discuss with study team – this may be criteria for cessation of intervention. Record as adverse event. If study team not immediately available (i.e. weekends, nights) wean infusion at discretion of attending responsible.
 - Caution with glucose once EMR is stopped – glucose management algorithm must continue to be followed.

d. Hyponatremia (Na <130)

- i. Additional sodium replacement (or diuresis) at discretion of primary team
- ii. If SIADH suspected and for fluid restriction – intervention has to be weaned. Caution with glucose once EMR is stopped(weaned) – glucose management algorithm must continue to be followed.

e. Severe Hypermagnesemia (Mg >4 mg/dl)

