9.0 CRITERIA FOR INTERVENTION DISCONTINUATION

These include:

- Patient's consent withdrawn
- Patient's discharge from the ICU
- Allergy to any of the components of EMR
- Patient requiring renal replacement therapy
- Patient's death
- Patient changed to Comfort Care status
- Patients receiving greater than 70% of their nutritional needs via enteral nutrition
- Unable to undergo placement of CVC for any technical reasons or withdrawal of CVC
- Severe fluid overload or electrolyte abnormality requiring discontinuation (as described in Chapter 7)
- Jehovah's Witness who decides not to accept albumin.
- If patient develops a known contraindication, or an unspecified condition where the clinician thinks the patient should be taken off the protocol, then there should be a discussion and treatment should be weaned according to safety protocol.

In case of discontinuation, please follow weaning procedure detailed in section 6.7.

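### Section 6.4 removes withdrawn and Comfort Care patients from the study after randomisation, against sections 7.2 and 9.0 and the randomised denominator, and no analysis set is defined

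*Combined protocol and SAP*

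**What the plan says.** **Who stays in the study.** Section 6.4 (Adherence Assessment) states: "Patients who have requested to be withdrawn from the study or achieve Comfort Care status during ICU stay will be removed from the study". The next sentence draws a contrast: "Those who die or begin renal replacement will be followed up but the interventions will be stopped". Section 9.0 has "Patient changed to Comfort Care status" in a list of reasons to discontinue the intervention, with no mention of follow-up. The outcome data list in section 7.2 ends by following all patients for up to 90 days. Section 8.2 says of a patient whose study fluid is stopped for severe fluid overload, "then the patient will be withdrawn", without saying whether from the infusion or from the study.

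**Who is analysed.** The summary table and section 10.2 describe 112 patients, 56 randomised to each arm. Section 10.3 uses the term full analysis set once, for those 112, and counts 28 randomised per arm at the interim. No membership rule is given, and nothing says what day-28 status a removed patient has.

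**When the clock starts and stops.** Section 1.1 states: "Twenty-eight day mortality is defined during the time from the day SC+EMR or SC was first administered". The summary table has the same rule for the primary endpoint: "defined during the time from the day SC+EMR or SC was first administered until a patient dies or is followed through 28 days". Standard care is described in section 6.1 as "follow institutional ICU management algorithm for septic shock", and "Vasopressor therapy needed to elevate MAP" is already an entry criterion in section 5.1. Section 7.1 records the time of shock onset and section 7.2 sets day 0 at recruitment, but neither is tied to the endpoint. For the time-to-event analysis of 28-day mortality, the summary table censors survivors at 28 days and section 10.5 at one month. Both allow up to 6 months for overall survival, against 90 days in section 7.2.

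**The concern.** The two sentences in section 6.4 separate patients who leave the study from patients who only stop the intervention, and they put Comfort Care in the first group. Section 5.2 excludes Comfort Care patients at entry, so that status can arise only after enrolment. The trial is unblinded, so the change of status is decided by a team that knows the allocation.

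If most such patients die by day 28 (an assumption, though a plausible one where expected mortality is 70%), removing them deletes primary events. If the decision is made at different rates or for different kinds of patient in the two arms, the arms left for comparison are no longer the randomised ones. The bias could favour either arm. The same question of who counts arises at the interim analysis.

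**Working it through.** **Inputs from the documents:** 28-day mortality 70% versus 40%, 56 per arm, two-sided chi-square at 0.05 (section 10.2); study solution to start within 12 hours of shock onset and of MICU admission (section 5.3). **Assumptions:** the number removed, their outcome, and the hazard shape. The documents give none of these.

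**1. The plan's own figure.** n = [1.960·√(2·0.55·0.45) + 1.282·√(0.70·0.30 + 0.40·0.60)]² / 0.30² = (1.379 + 0.860)² / 0.09 ≈ 55.7, so 56 per arm. Power at 56 per arm is 0.902 (exact binomial 0.896). The stated 112 and 90% reproduce, with no allowance for losses.

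**2. Deaths removed from one arm only, no true effect.** Expected deaths are 0.70 × 56 = 39.2. After removing m patients who would die, the rate is (39.2 − m)/(56 − m).

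| m | Rate | Drop (points) |
|---|---|---|
| 1 | 38.2/55 = 0.695 | 0.5 |
| 2 | 37.2/54 = 0.689 | 1.1 |
| 4 | 35.2/52 = 0.677 | 2.3 |
| 6 | 33.2/50 = 0.664 | 3.6 |

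**3. False-positive rate.** A fraction r of one arm is removed, all of whom would die, so that arm's rate becomes (0.70 − r)/(1 − r). The rejection rate is the exact binomial sum over all tables with |z| > 1.96.

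| r in one arm | n per arm | Rates | Two-sided rejection |
|---|---|---|---|
| 0 | 56, 56 | 0.700, 0.700 | 5.1% |
| 10% | 56, 50 | 0.700, 0.667 | 6.5% |
| 20% | 56, 45 | 0.700, 0.625 | 13.0% |

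**4. Removal in both arms, design effect true.** The result depends on the model.
- Same share q of deaths removed, rate p(1 − q)/(1 − pq). For q = 10, 20, 30% the difference stays near 30 points, analysed N falls to about 106, 100, 94, and power to 0.89, 0.87, 0.84.
- Same share r of patients removed, all dying. For r = 10, 20, 30% the difference widens to 33.3, 37.5, 42.9 points and power rises to 0.93, 0.96, 0.99.

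Balanced removal can therefore lower power or inflate the apparent effect.

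**5. Clock start (minor).** Under a constant hazard F(t) = 1 − 0.30^(t/28). A 12-hour delay with all deaths kept gives F(28.5) − F(28) = 0.6 points; 3 and 6 hours give 0.2 and 0.3.

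**6. One month instead of 28 days (minor).** Under the same model in each arm, F(30) is 72.5% versus 42.2%, a difference of 30.3 points; at day 31 it is 30.4. The design difference is 30.0.

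**The case against.** The best reply is that section 6.4 concerns adherence and nowhere says that removed patients leave the mortality analysis. Section 7.2 follows all patients to 90 days. Section 9.0 lists Comfort Care, and also severe fluid overload, as reasons to stop the intervention. The summary table, section 10.2 and section 10.3 all count randomised patients. On that reading everyone is analysed and section 6.4 is loose wording.

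Much of this stands. A reader might infer that the plan excludes Comfort Care patients from the primary test; the documents do not settle that, they contradict themselves. What remains is that section 6.4 sets removal against follow-up in adjoining sentences, and no membership rule or day-28 status overrides it.

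A reader might also infer that standard care has no usable start time, or that patients allocated to the intervention but never infused would be dropped. Neither is supported. Shock onset and recruitment day are recorded for both arms and merely need linking to the endpoint, and no text drops uninfused patients. The 12-hour window keeps the timing error small. Nor does the one-month wording threaten the primary result: the chi-square endpoint is fixed at 28 days in section 1.1.

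**Conclusion.** Section 6.4 is wrong as written and conflicts with sections 7.2 and 9.0 and with the randomised denominator. The conflict in the text is certain. The size of any bias is not, because the documents give no removal rate and do not say how Comfort Care patients fare.

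If a handful of deaths were removed from one arm, its rate would move by 0.5 to 3.6 points. An imbalance of 10% or 20% of one arm, all dying, would take the false-positive rate to about 6.5% or 13%. These are illustrations, not forecasts, and no direction of bias can be claimed. The sample size calculation itself is correct.

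The clock start (at most about 0.6 points for a 12-hour delay under constant hazard) and the two follow-up limits are minor. The 6-month limit concerns secondary overall survival only.

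**What to change.** **Main change**
- In section 6.4, separate stopping the intervention from leaving the study.
- In section 10.3, define the full analysis set as all randomised patients in their assigned arm, whether or not infusion started, and refer to it in section 10.5.
- Keep Comfort Care patients in the 28-day and 90-day mortality analyses, and withdrawn patients as far as their consent allows.
- Report the number of and reasons for losses by arm.
- Reconcile sections 6.4, 8.2 and 9.0 on follow-up once the intervention has stopped.

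**Minor changes**
- In section 1.1, the summary table and section 10.5, set time zero at randomisation in both arms. Align the second secondary objective, which refers to the time after diagnosis of septic shock.
- In section 10.5, change one month to 28 days.
- State a single censoring limit for overall survival, reconciling 90 days with 6 months.

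**Cost.** This is mostly wording, and N = 112 stays. Vital status at days 28 and 90 must be recorded for patients who stop the intervention or move to Comfort Care. Counting from randomisation and including uninfused patients may dilute the effect slightly. Power stays near 0.90 only if few day-28 statuses are lost.

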2.0 BACKGROUND

2.1 Definitions

Sepsis is defined as a life-threatening condition, which is triggered by an exaggerated and unregulated response of the body to an infection. Septic shock consists of the state of sepsis where, in addition to the unregulated response, cellular, metabolic, and circulatory alterations lead to a marked increase in mortality(1). Previously the spectrum of the disease was divided into sepsis, severe sepsis and septic shock, where severe sepsis was defined as acute organ dysfunction secondary to documented or suspected infection(2). However, in the third international consensus for sepsis and septic shock (Sepsis -3) it was determined that the term severe sepsis was redundant and therefore it was decided only to use the diagnoses of sepsis and septic shock(1). Even so, today most retrospective epidemiological studies continue to use the term severe sepsis in their analysis, but this is expected to change over time.

2.2 Epidemiology

Worldwide, 19 million cases of sepsis are calculated each year, however, it is presumed that this value may be even higher due to under reporting, which is considered high in low- and middle-income countries (3,4). According to the report of the Center for Disease Control and Prevention (CDC) of 2017, sepsis annually affects 1.5 million individuals in the United States, of whom 250,000 die (5), which includes it among the top 10 causes of death in the US. This generates annual costs of over 24 billion dollars(6); which makes this condition a public health priority.

In a recent study not yet published performed by [name] et al. in 2017, a sample of 305 patients (154 with hematologic malignancies and 108 with solid tumors) with the diagnosis of septic shock hospitalized in the ICU of The University of Texas MD Anderson Cancer Center were assessed. It was found that the 28 day mortality was 70%. These values shed light on the emergent requirement of seeking treatment alternatives that may improve outcomes in these patients.

2.3 Pathophysiology

The normal response of the host to an infection is a complex process in which a microorganism is localized and controlled, while injured tissue repair processes are undergoing. When the inflammatory response is activated, proinflammatory mediators (tumor necrosis factor-alpha (TNFa), IL-1, IL-2, IL-6, among others) chemokines such as ICAM-1 and VCAM-1, and nitric oxide (NO) are released. The proinflammatory cytokines generate the activation and recruitment of cells of the immune system. Also the production of anti-inflammatory mediators such as IL-10 and IL-8 modulate the response and lead to homeostasis (8). Sepsis results when the response becomes generalized and uncontrolled, affecting normal tissue distant from the original site of infection. The mechanisms that lead to the unregulated response are not well known, however several studies have shown how the components of the causative organism may be involved in the way in which the immune system is stimulated (endotoxins, peptidoglycans, muramidase, dipeptidase and lipoteichoic acid, among others) (9,10). Likewise, studies have pointed out the possibility that there is a genetic susceptibility for the development of more severe responses, and worse outcomes (11).

The release of proinflammatory cytokines causes fever, hypotension, leukocytosis and the induction of other cytokines. In addition, there is an activation of the coagulation cascade and fibrinolysis. TNFa plays a key role in the disease and some studies have shown a significant increase in patients with septic shock (12). Nitric oxide is a biological molecule produced by a large number of cells. It is involved in several pathological processes and has been described as having both beneficial and harmful effects at the cellular and vascular level (13). At the cellular level NO generates nuclear damage, alterations of proteins and phospholipid membranes, and the inhibition of cellular respiration in several cell types. At the same time, it has been shown that NO can also reduce free oxygen radicals, generating a decrease in cell damage. Therefore its total inhibition as a therapeutic measure does not seem to be an adequate intervention and in fact it has been proven in clinical studies that the use of inhibitors of nitric oxide synthase (NOS) can increase mortality(14).

In the early septic phase, cellular metabolism is upregulated with systemic inflammation which leads the organism to enter into a hypermetabolic state (15). This is mainly caused by the requirement of supra physiological energy to deal with fever, amplified protein synthesis, tachycardia and tachypnea(16). It is estimated that basal energy requirements for a septic patient could reach up to 10,000 calories per day (17). This critical need for supplemental nutrients may not be met since it occurs under critical illness (thermodynamically closed system in which metabolic substrates are not administered to the patient) (16). This hypermetabolism also produces a large amount of toxic cellular by-products, such as hydrogen peroxide (H₂O₂), which under normal conditions, is well degraded by the enzyme glutathione peroxidase. In critically ill patients, glutathione is commonly depleted and there is a significant increase in H₂O₂, cellular toxicity occurs, and a greater decrease in glutathione stores can be observed (18,19). In fact, low levels of glutathione have been indirectly related to increased mortality even after the subject survived the infectious insult(20).

After the above-mentioned process has been established, inflammatory products, such as nitric oxide and the reactive nitrogen species, can cause mitochondrial dysfunction due to the inhibition of the electron transport chain by direct blocking of respiratory enzymatic complexes, causing oxidative stress damage, and promoting mitochondrial DNA breakdown. All of these processes lead to a decrease in mitochondrial function in terms of the use and production of ATP, which triggers cytotoxicity and hypometabolism in the late phase of the disease. This has been described as a hibernation-like state where the organs reduce their metabolism in an attempt to survive the inflammation caused by sepsis (21).

The clinical relevance of mitochondrial dysfunction in septic shock has been studied extensively. In a study of 28 septic shock patients who underwent a skeletal muscle biopsy at 24 hours after ICU admission, the ATP concentrations in the muscle (a marker of mitochondrial oxidative phosphorylation) were significantly lower in the 12 patients who died compared to the 16 who survived. Additionally, there was an association between overproduction of NO, decrease of antioxidants and the severity of the clinical outcome

(22). This led to the conclusion that the cellular lesions were due to dysoxia, which is the inability to use the oxygen even under the presence of adequate concentrations. This is also known as oxygen limited energy depletion. Strikingly, in studies of patients who died from septic shock, both electron microscopy and immunohistochemical markers revealed that cell death was rare in septic patients with cardiac and renal dysfunction. The degree of cell injury or death was not related to the severity of the organ dysfunction. It was then considered that the presence of morphological changes in the mitochondria would explain the energetic crisis that results in organ dysfunction in the absence of cell death (23). This reinforces the theory that this hibernation-like response may initially start as a mechanism of cell survival, but ultimately ends in multi-organ dysfunction and death.

